### 4.4 Cost Analysis

Cost was reported at the site-level. To calculate the incremental cost effectiveness ratio we assigned to each participant the average cost per person at their study site and within their treatment arm. We treated this value as if it was the participant's realized cost. This was then used in a complete case analysis comparing the mean cost difference between participants on P3+ vs P3 divided by the mean efficacy difference as measured by the binary TFV measure at 3 months. To create a 95% confidence interval we used the percentile bootstrap method.

Table 7: Super Learner Libraries and variables used for the propensity score and outcome regressions

Model	Outcome	Learner(s)	Baseline Variables 
$\bar{g}_{\Delta Y_j}(a, w_0)$	Self-Reported PrEP use or Exploratory Outcome of Interest Observed	SL.glm	BEO  , BEO*trt
			Age, BEO, On PrEP, Site, Race/Ethnicity
		SL.earth	Age, BEO, on PrEP, Site, Race/Ethnicity, (BEO * On PrEP), (Age*trt)
			Age, BEO, on PrEP, Site, Race/Ethnicity
		HAL	Age, BEO, on PrEP, Site, Race/Ethnicity
		glmnet	Age, BEO, on PrEP, Site, Race/Ethnicity, (BEO * On PrEP), (Age*trt)
$\bar{Q}_k^j(w_0)$	Self-Reported PrEP use or Exploratory Outcome	SL.glm	Age, BEO, on PrEP, Site, Race/Ethnicity, (BEO * On PrEP), (Age*trt)
			Age, BEO, on PrEP, Site, Race/Ethnicity
		SL.earth	Age, BEO, on PrEP, Site, Race/Ethnicity
			Age, BEO, on PrEP, Site, Race/Ethnicity
		HAL	Age, BEO, on PrEP, Site, Race/Ethnicity
		glmnet	Age, BEO, on PrEP, Site, Race/Ethnicity, (BEO * On PrEP), (Age*trt)
Treatment		step	Age, BEO, on PrEP, Site, Race/Ethnicity, (BEO * On PrEP), (Age*trt)

trt -

Treatment

BEO - Exploratory measure at baseline

 Baseline variables to include in the model, in addition to dummy variables for treatment

 If the outcome of interest is available at baseline, it will be controlled for. If not, another variable may be controlled for, if it is predictive for both the EO and missingness.

Table 8: Hypotheses and P-Value Significance Thresholds

Study Objective	Hypothesis	Significance Threshold
Primary	There is no difference between P3/P3+ and SOC in terms of PrEP adherence, as measured by binary FTC-tp.	0.05
	There is no difference between P3/P3+ and SOC in terms of PrEP adherence, as measured by binary TFV-dp.	
Secondary II	There is no difference between P3/P3+ in terms of self-reported weekly PrEP use.	0.025
	There is no difference between P3/P3+ in terms of self-reported monthly PrEP use.	
Secondary III	There is no difference between P3/P3+ and SOC in terms of self-reported outcome.	Benjamini-Hochberg

Table 9: Baseline variables stratified by treatment group (Table 1)

Variable	P3 (N= )	P3+ (N= )	SOC (N= )
Symmetric Baseline Variables, mean (SD)			
Skewed Baseline Variables, median (Q1,Q3)			
Categorical Baseline Variables, count (%)			

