5.4.3 RCT

Recruitment for the RCT will occur in nine SRV cities/locales (Atlanta, Georgia; Boston, Massachusetts; Bronx/NY, New York; Chapel Hill, North Carolina; Charlotte, North Carolina; Chicago, Illinois; Houston, Texas; Philadelphia, Pennsylvania; Tampa, Florida). Identifying, screening and enrolling potential participants for the RCT will proceed as described in Sections 4.3, 4.4, 4.5 and 5.1.

After eligibility is confirmed and consent/assent is obtained, whole blood specimens will be collected. Participants will then complete a CASI survey (Alchemer) and be randomized into a study arm. Next, participants will be walked through a brief description of their respective study arm (Control Group Script, P3 Intervention Group Script and P3+ Intervention Group Script). Participants will be compensated \$50 at the conclusion of the enrollment visit, and reminded that they will be asked to complete 3 and 6 month follow-up surveys and specimen collections. Participants completing procedures remotely will be compensated \$50 for specimen collection and \$50 for visit activities (i.e.

surveys, intervention onboarding). For participants completing their RCT enrollments remotely via phone or video teleconference, eligibility confirmation and consent/assent will happen prior to their blood specimen collection, baseline survey completion, randomization, and overview of study arm.

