5.4.5 Intervention Monitoring/Quality Control

Because the P3 intervention is an app, intervention fidelity is assured (i.e., all participants will receive the intervention in the same way and have access to all of the same resources). P3+ will include provision of Next Step Counseling (NSC), an interactive, client-centered motivational intervention to improve PrEP adherence, delivered via texting through the app. A NSC protocol will be developed during formative work and implemented in field testing and the RCT. During the RCT, we will review 20% of sessions every quarter. The adherence counselor(s) will document all sessions on the fidelity form developed by the NSC research team.⁴² [name] will assess quality and fidelity by reviewing counseling transcripts and the accuracy of fidelity forms. [name] will retrain the counselor(s) if any quality or fidelity issues are detected.

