of a priori and emergent themes including operational definitions of all codes and sample quotations to illustrate how to apply each code. Two study team members will then use the codebook to independently code the compiled user profiles while a third team member will review these sections of coded data and resolve discrepancies. We will draw a random sample of 20 instances for the coders to begin with and calculate an inter-rater reliability score based on their code assignments. If this score is <95% we will refine the codebook definitions and retrain the coders. Coders will then complete the coding of the remaining instances and we will calculate an inter-rater reliability score. Discrepancies will then be reviewed and resolved by the research team. We will use Dedoose software to assist with theme identification, coding textual data, and describing relationships among codes (via code co-occurrence and memoing functions).⁵⁶ Coding and analytic activities will be discussed during weekly team meetings. Our study team has successfully used all of these methods in past projects with HIV+ YMSM.^{20,57,58}

Cost-comparison between the two intervention study arms: Incremental cost effectiveness ratio (ICER) between the two intervention arms will be defined as $\Delta C / \Delta E$, where ΔC denotes the estimated difference in mean costs of the intervention and ΔE reflects the estimated difference in mean effectiveness between the interventions. ICER will be calculated for outcomes in which the intervention is non-dominated. Cost was measured at the site level. We will calculate ΔC using the mean of costs for each intervention arm. Similarly, we will calculate ΔE using the mean of efficacy measurements for each intervention arm. We will also analyze individual level counseling costs with TMLE if there is substantial variation in time spent on counseling between participants.

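### The ICER bootstrap uses site-by-arm average costs as individual costs and names no resampling unit: read as a participant bootstrap, it probably understates cost uncertainty, with a smaller effect on the ICER interval

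*SAP*

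**What the plan says.** SAP 4.4 starts from "Cost was reported at the site-level". For the ICER, "we assigned to each participant the average cost per person at their study site and within their treatment arm", and then: "We treated this value as if it was the participant's realized cost". In a complete-case analysis, the P3+ minus P3 difference in mean cost is "divided by the mean efficacy difference as measured by the binary TFV measure at 3 months". On uncertainty the section has one sentence: "To create a 95% confidence interval we used the percentile bootstrap method". It gives no resampling unit, no stratification of the resampling, and no allowance for costs being known only as site averages.

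Protocol 10.3.4 also measures cost at site level and compares mean costs by arm. It adds a conditional analysis: "We will also analyze individual level counseling costs with TMLE if there is substantial variation in time spent on counseling between participants". SAP 4.4 neither carries this over nor says that the condition was examined. On the data available, Protocol 5.4.5 says "The adherence counselor(s) will document all sessions on the fidelity form developed by the NSC research team", and Protocol 10.3.4 lists the number and content of P3+ sessions among the data to be collected. On the number of cost units, Protocol 5.4.3 says "Recruitment for the RCT will occur in nine SRV cities/locales".

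**The concern.** A bootstrap interval reflects only the variation in the values that are resampled. Once each cost is replaced by its site-by-arm mean, participants at the same site and arm have identical costs. A bootstrap over participants then counts one site average many times, as if each copy were new information, and it loses most of the spread between participants within a site. For P3+ that spread matters. Counselling is what separates P3+ from P3, and the protocol expects uptake to differ: its definition of high and low P3+ users in 5.4.3 turns partly on having three or more sessions.

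The second study hypothesis (Protocol 2.3) says that P3+ will cost more, so the numerator of the ratio is of interest in its own right. If its uncertainty is understated, the extra cost looks better known than nine site-level figures per arm can justify.

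**Working it through.** **Inputs from the documents.** 80 participants per arm; nine sites; randomization stratified by site; 20% expected loss. The plan's own sample figure reproduces: 240 × (1 − 0.20) = 192, and 192 / 3 = 64 per arm. SAP 6.2 expects high DBS missingness, so the complete-case number may be below 64.

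**Assumptions.** The documents give no cost SD and no split of cost variance between and within sites. Write ρ for the between-site share of cost variance within an arm, and m for participants per site and arm. With equal sites m = 80/9 = 8.9.

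**Step 1: against individual costs.** Per arm, a participant bootstrap of assigned averages has variance of about SD² × [ρ + (1 − ρ)/m] / n. Individual costs would give SD² / n. The SE ratio is about √[ρ + (1 − ρ)/m]:
- ρ = 0: √(1/8.9) = 0.34
- ρ = 0.20: √(0.20 + 0.80/8.9) = 0.54
- ρ = 0.50: √(0.50 + 0.50/8.9) = 0.75

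About 1/9 of the within-site variance therefore survives, along with all the between-site variance.

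**Step 2: against the true sampling error, sites random.** With independent site-by-arm effects, the true variance per arm is SD² × [ρ/9 + (1 − ρ)/80], which equals (SD²/9) × [ρ + (1 − ρ)/8.9]. The bootstrap divides the same bracket by 64 instead of 9, and the spread of nine means about their own average contributes a factor 8/9. The SE ratio is √(9/64 × 8/9) = √(8/64) = 0.35, whatever ρ is.

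**Step 3: simulation** (nine sites, 80 enrolled and 64 analysed per arm, 3000 replicates per setting). Entries are the SE from a participant bootstrap of assigned averages, divided by the SE named in the column.

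| ρ | individual-cost bootstrap | true SE, sites random | true SE, sites fixed |
|---|---|---|---|
| 0 | 0.31 | 0.34 | 0.34 |
| 0.05 | 0.37 | 0.35 | 0.42 |
| 0.10 | 0.42 | 0.34 | 0.49 |
| 0.20 | 0.51 | 0.34 | 0.63 |
| 0.50 | 0.72 | 0.35 | 1.03 |
| 0.90 | 0.95 | 0.35 | 1.86 |

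With random sites, a nominal 95% interval for the cost difference covered about 40-54%.

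**Step 4: the interval the SAP reports.** Assume a cost difference of 100, cost SD 75, 64 per arm and a P3 response of 0.40. The SE of the effect difference is about √(2 × 0.40 × 0.60 / 64) = 0.087. ICER intervals at ρ = 0.05:
- Effect difference 0.20: 258 to 2150 (assigned averages) against 240 to 2201 (individual costs). Widths 1892 and 1961; 1892/1961 = 0.96, about 4% narrower.
- Effect difference 0.30: 211 to 740 against 196 to 762. Widths 529 and 566; 529/566 = 0.93, about 7% narrower.

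At ρ = 0.50 the better comparison is an SE that respects sites. At an effect difference of 0.30 the intervals are 205 to 747 against 140 to 807. Widths 542 and 667; 542/667 = 0.81, about 19% narrower.

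Further simulation put the shortfall against individual costs at about 2-9% for a cost CV of 0.6 and up to about 22% for a CV of 1.0.

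**The case against.** The strongest reply is that the SAP never says participants are resampled. If whole sites were resampled, most of the difficulty disappears. That is possible, but the text treats the assigned value as the participant's own and compares participants on P3+ with participants on P3. Resampling participants is the natural reading, and the sentence needs completing either way.

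The second reply is that the planned interval is for the ICER, not for the cost difference. This stands. A reader might infer from the cost component that the ICER interval is several times too narrow; the calculations do not support that, because uncertainty in the TFV difference dominates.

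Third, the nine sites are named and serve as randomization strata, so treating them as fixed is defensible. This also stands in part. With fixed sites the cost interval is too narrow only when the between-site share is low, and it becomes too wide when the share is high. Nor do the resamples carry almost no cost variation, as a reader might suppose: even with no true site differences the SE is 31% of its individual-cost value.

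Fourth, a reader might infer that the SAP dropped a required individual-cost analysis. The protocol's main method is also site-level and the individual analysis was conditional. The documents do not show that the condition was met. What remains is that the SAP does not mention the condition.

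Finally, the second hypothesis has no test in SAP Table 8, and SAP 5.2 reports untested comparisons descriptively. That limits the consequence, but a reported 95% interval should still mean what it says.

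**Conclusion.** The point holds for the cost component and is modest for the ICER. SAP 4.4 leaves the resampling unit open. On its natural reading it treats at most nine cost values per arm as up to 80 independent observations. The SE of the cost difference is then about one third of the correct value if sites are random, or if they are fixed and the between-site share is near zero. With fixed sites the understatement shrinks as that share grows, and it reverses from a share of about 0.5.

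The ICER interval is about 2-9% too narrow relative to individual costs at an assumed CV of 0.6, and up to about 22% at CV 1.0. All these sizes rest on assumed cost variances, roughly equal sites and a participant bootstrap; the documents supply none of the cost figures. The matter affects the cost objective only and leaves the primary efficacy analysis untouched. It should be corrected.

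**What to change.** In SAP 4.4:

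1. State that the bootstrap resamples sites, keeping both arms of a site together, then participants within site and arm, and recomputes the ICER each time. The site stage carries the cost uncertainty, including sampling error in the site means. The participant stage adds uncertainty in the TFV difference.
2. Report the P3+ minus P3 cost difference with its own interval.
3. Label the cost information as resting on nine sites and note that coverage may stay somewhat below 95%. In simulation, site resampling covered about 85-91%.
4. Where the documented P3+ session counts allow, add the individual counselling-cost analysis from Protocol 10.3.4, still resampling by site; otherwise state that its condition was checked and not met.

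Building individual costs and bootstrapping participants within arm would not be enough. That covered only 83-91% at a between-site share of 0.1 and about 62% at 0.5. It may also need session durations, which the documents do not say were recorded.

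The cost is a few sentences in the SAP, a small rerun and a wider interval. Items 1 to 3 use data already in hand.

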## 4 Analysis Plan

For all of the above objectives, targeted minimum loss-based estimation (TMLE) will be used to estimate the mean counterfactual outcome for the population of interest, under each treatment, and at each time point (3 months and 6 months). For binary variables we will estimate the proportion or probability of the outcome.

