## 6.2 Missing Data and Modification of Primary Analysis

Due to COVID-19, the collection of dry blood spots (DBS) was interrupted during this study. Therefore, the missingness in DBS will be high and it is possible for patients to have follow-up survey data, while missing the DBS follow-up data, or vice versa. Although TMLE can accommodate missingness at random (conditioned on baseline covariates) in the outcome of interest, a high amount of missing data in DBS will increase the variance of the estimator. Therefore, we decided to use survey data to “impute” the outcome variable. In doing so, we also require additional regression models to build the estimator for ATE. Please refer to the Supplement for details.

There are two survey variables that will be used to impute the values of the DBS data, namely PrEP use in the past week (number of days) and PrEP use in the past month (reported as a percentage of days). If the patient reported that they are *not* currently on PrEP, then the weekly PrEP use is assumed to be zero.

It is possible for one survey question to be present, but the other to be missing. In these cases we will use three simple forms of imputation to deal with the missing survey variable:

1. We will use mean imputation. First we stratify by current PrEP use (Y/N) and then within each group we perform mean imputation for the missing variable.
2. We will predict the survey variable (weekly or monthly PrEP use) with the other survey variable that is present using simple linear regression models
3. To impute weekly PrEP use from monthly PrEP use, we scaled the participant’s month variable to range from 0-7. Similarly to impute monthly PrEP use from weekly PrEP use, we scaled the participant’s week variable to range from 0-100.

Once this imputation is performed we can build a super learner library that includes each of the imputation methods and allow the super learner to pick the “best” methods via giving them weight in the final learner.

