### 6.3 Confounder Selection

Since treatment was randomized in this study, our primary concern is controlling for confounders that affect both whether patients remain in the study and whether patients adhere to PrEP.  $W_0$  and  $W_1$  are potentially high-dimensional vectors, therefore, it is best advised to select a subset of the covariates to control for in the analyses. Factors identified by the study team that predict PrEP adherence are: age, race/ethnicity, PrEP stigma, substance use, mental health, prior PrEP use, PrEP self-efficacy, partner serostatus, and sexual behavior. In the interest of parsimony, we selected age, baseline DBS, site, race/ethnicity, and baseline PrEP use (yes/no) as the variables to control for in our analysis.

It is possible that there are time-varying confounders of the missingness/outcome relationship. Unfortunately, we cannot account for these confounders for our analysis of the three month time point. For the six month outcome, a confounder of the missingness/outcome relationship may be PrEP use at three months. One assumption of our primary analysis, is that this confounding does not exist or is negligible.

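### The ICER is computed on complete cases, although the SAP expects high DBS missingness and already plans TMLE estimates for the same arms and outcome

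*SAP*

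**What the plan says.** SAP 4.4 gives each participant the average cost for their site and arm. It continues: "This was then used in a complete case analysis comparing the mean cost difference between participants on P3+ vs P3". For the denominator, efficacy is the 3-month TFV result scored as protective or not. The interval is specified as "To create a 95% confidence interval we used the percentile bootstrap method".

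Other parts of the SAP point to a different treatment of missing blood results:

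- SAP 4, which follows the cost objective in 3.3, opens: "For all of the above objectives, targeted minimum loss-based estimation (TMLE) will be used".
- Table 6 defines the cost estimand as E[C(a2b) − C(a2a)] / E[Y(a2b) − Y(a2a)], a ratio of counterfactual contrasts between P3+ and P3.
- SAP 6.2 states: "Therefore, the missingness in DBS will be high". It adds that "a high amount of missing data in DBS will increase the variance of the estimator", and brings in self-reported PrEP use for that reason.
- SAP 6.3 states that "our primary concern is controlling for confounders that affect both whether patients remain in the study and whether patients adhere to PrEP".
- Secondary objective I and Table 11 give P3 vs SOC and P3+ vs SOC for TFV-dp at 3 months. Table 16 lists the primary and secondary analyses as those that incorporate survey data.

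The protocol is less specific. Section 10.3.4 takes ΔE from arm means and names no missing-data method. Section 10.4 reserves complete-case analysis for small losses and has self-report inform the TMLE when FTC-TP or TFV-DP is often missing. It also allows complete cases or imputation to be considered in other analyses.

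**The concern.** The SAP identifies the missing-data problem, adopts a method for it, and applies that method to these two arms and this outcome. It then sets the method aside for the ICER without giving a reason.

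Two things are at stake. First, subtracting the two contrasts in Table 11 cancels the SOC mean and gives a P3+ minus P3 difference. The ICER would use another value for the same quantity. Second, ΔE is the denominator of a ratio. If blood return relates to adherence in one way under P3+ and another under P3, a modest error in ΔE can multiply the ICER or change its sign.

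The cost side has a smaller version of the problem. Cost is assigned by site and arm, so no TFV result is needed to compute ΔC. If 4.4 also restricts ΔC to participants with a TFV result, which is the natural reading but is not stated, mean cost is weighted towards sites that obtained more blood samples.

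**Working it through.** **Inputs from the documents.** 80 per arm; 20% planned loss by month 3; SOC adherence of about 27% at month 3; a 14-point effect (all protocol 10.2.3 or the abstract); 56% protective levels at week 4 in the background cohort (protocol 1.1). No DBS missing percentage is given, so 20% to 60% is assumed.

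**1. The plan's own figure.** 240 × (1 − 0.20) = 192, and 192 / 3 = 64 per arm. This reproduces. It is the only stated figure that bears on the point; no expected ICER or ΔE is given.

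**2. Precision.** For two arms with n = 80(1 − m) observed, SE(ΔE) = √(2p(1 − p)/n). Suppose blood is missing completely at random and baseline and survey data, observed for everyone, explain a share R² of outcome variance. An estimator using them has variance (1 − R²) + (1 − m)R² relative to complete cases.

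Take p = 0.41 (27% + 14 points) and m = 0.50, so n = 40. Then SE = √(2 × 0.41 × 0.59 / 40) = 0.110, and the 95% half-width is 1.96 × 0.110 = 0.216.

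| R² | Relative variance | Half-width |
|---|---|---|
| 0.1 | 0.95 | 0.210 |
| 0.3 | 0.85 | 0.199 |
| 0.5 | 0.75 | 0.187 |

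The variance reduction is 2% to 10% at m = 0.20 and 6% to 30% at m = 0.60. For p from 0.27 to 0.56, the complete-case half-width is 0.154–0.172 at 20% missing, 0.195–0.218 at 50% and 0.218–0.243 at 60%. Survey data are themselves incomplete, so the gains are upper values for each R².

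**3. Bias when missingness depends on a measured baseline factor (assumed).** The factor splits each arm in half. P3 adherence is 20% / 60% in the two halves, and P3+ is higher by the true ΔE in each. The complete-case arm mean is Σ(adherence × retention) / Σ(retention).

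- Retention 40% / 60% in both arms, true ΔE 0.10: 0.54 − 0.44 = 0.10. No bias.
- P3 50% / 50%, P3+ 40% / 70%, true ΔE 0.10: (0.3 × 0.4 + 0.7 × 0.7)/1.1 − 0.40 = 0.155. With ΔC unchanged, the ICER is 0.65 times its true value.
- P3 30% / 70%, P3+ 50% / 50%, true ΔE 0.10: 0.50 − 0.48 = 0.02. The ICER is 5 times its true value.
- Same retention, true ΔE 0.05: 0.45 − 0.48 = −0.03. The sign reverses.

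**4. Simulation under the same kind of missingness.** 4,000 trials, 80 per arm, true ΔE 0.10, retention 50% / 50% in P3 and 35% / 70% in P3+, with a doubly robust estimator standing in for TMLE and self-report observed for all.

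| Estimator | Bias | RMSE |
|---|---|---|
| Complete case | +0.070 | 0.129 |
| Baseline-adjusted | +0.001 | 0.109 |
| Baseline and self-report | +0.001 | 0.101 |

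With 50% missing completely at random, none of the three was materially biased. Variance relative to complete cases was 0.92 with baseline adjustment and 0.80 with self-report added.

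**5. Bias when return depends on adherence itself (assumed).** Let 45% be adherent in both arms, so true ΔE is 0. Adherent participants return blood 70% of the time; non-adherent participants return it 60% of the time in P3+ and 40% in P3. Complete cases give 0.315/0.645 = 48.8% against 0.315/0.535 = 58.9%, a false −10.0 points. Suppose adjustment uses a self-report observed for all, with 90% sensitivity and 60% specificity. The adjusted means are 47.8% and 54.9%, so −7.1 points remain. At 90% / 90%, −3.7 remain.

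**The case against.** The strongest case for leaving 4.4 alone has four parts.

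- **No evidence of differential return.** SAP 6.2 attributes the missing DBS to COVID-19. Nothing ties that to arm, randomization is stratified by site, and follow-up reminders run through study staff and SMART Web for everyone. The documents give the P3+ counselor no role in specimen collection. This stands: the arm-differential scenarios above are assumptions.
- **TMLE is not a cure.** Its independence assumptions (SAP A.2, Table 16) fail if return depends on adherence beyond what covariates and self-report capture. Step 5 shows most of the error can then remain. This also stands.
- **The documents leave some room.** SAP 4.2 ties TMLE with super learning to the primary and secondary objectives and does not mention cost. Protocol 10.3.4 uses plain arm means, and 10.4 allows complete cases to be considered in other analyses. This stands in part: the same section discourages complete cases when the loss is substantial, and SAP 4 and Table 6 still disagree with 4.4.
- **Low stakes and late timing.** Cost is the last-listed objective and has no hypothesis test. The revision history dates 4.4 to July 2022, while SAP 6.1 puts the analysis as done in April 2022. The change is therefore a re-analysis. That affects labelling and effort, not which estimator is better supported.

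A reader might infer that the reported ICER is biased, that TMLE would remove the bias, or that 4.4 breaches the protocol. The documents support none of these.

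**Conclusion.** The point holds as an internal inconsistency and an avoidable weakness. The complete-case ICER departs from SAP 4 and Table 6 without explanation, and its denominator need not match the difference implied by Table 11. Under the SAP's own missing-at-random assumptions, the survey-augmented TMLE is the better-supported source for ΔE.

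The bias examples show exposure only. Error in ΔE runs from 0 to about ±0.08, depending on assumed retention patterns that the documents neither confirm nor exclude. The precision gain is moderate, 5% to 25% of variance at an assumed 50% missing with R² of 0.1 to 0.5. The half-width for ΔE stays near 0.19 to 0.21 at p = 0.41, so neither version makes a P3+ vs P3 ratio precise. This is a recommended change at modest cost; it does not invalidate the trial's main results.

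**What to change.** In SAP 4.4:

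1. Take ΔE = P[Y(a2b)] − P[Y(a2a)] for TFV-dp at 3 months from the A.5 TMLE used for Secondary objective I, so that it agrees with Table 11.
2. Take ΔC over all randomized P3 and P3+ participants, and state this explicitly.
3. Bootstrap the whole procedure, refitting the TMLE in each resample.
4. Report the complete-case ICER alongside as a sensitivity analysis.
5. Reconcile 4.4 with SAP 4 and Table 6 in a sentence, and label the change as made after the analysis was done.

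No new data are needed. The cost is the re-analysis and computing time, since each bootstrap resample refits a multi-step TMLE with 10-fold super learning.
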